2.6. Estimated size

It is estimated that approximately 110 people will be recruited to the clinical trial each year. This number is based on the fulfilment of performance and quality indicators report of cerebrovascular care at the Centre for Highly Specialized Patient Care for Stroke Patients at Thomayer Hospital 2019. A total of 210 people is expected to be enrolled in the clinical trial over a period of two years (Figure 2), corresponding to a required sample number of 70 patients per group. This value is necessary in order to detect a significant difference in improvement

between two groups when achieving a mean difference effect (Cohen's d = 0.5), a significance level of $\alpha = .05$ and a strength of $1-\beta = .80$. The sample size was determined based on the minimal clinically significant change on a Berg balance scale (96).

Figure 2: Planned recruitment and randomisation process

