2.1. Clinical trial design

This will be a Four-Arm Parallel-Group Randomised Double Blinded Controlled Trial with a longitudinal design. Patients who fulfilled inclusion criteria will be randomly assigned to one of the four research groups (Group 1, 2, 3 or 4). Three groups will undergo an inpatient COMIRESTROKE (4 hours/day for 3 weeks). Group 1 (COMIRESTROKE – ICF) will undergo individualised rehabilitation therapy embodying the ICF system as a therapeutic tool, where current needs and wishes of the person after IS are integrated into an interdisciplinary team rehabilitation programme management. Group 2 and 3 will undergo a standard comprehensive intensive rehabilitation program three hours per day (39) plus one hour of specific PT (an individual neuroproprioceptive "facilitation inhibition" for Group 2, a technology-based training for Group 3). Group 4 will undergo standard care and will serve as comparative one to the intensified intervention groups.

Participants will be examined four times (Figure 1). At the beginning and after three weeks of hospitalization (both primary, secondary outcomes and a blood draw will be obtained for total RNA extraction, cDNA synthesis and real-time QPCR assessment of lncRNA candidates previously identified as potential therapeutic influencers in ischemic stroke), and then three months and one year after the end of the program (primary outcomes only).

Figure 1: Design of the study

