2.2. Eligibility criteria and subgroups

Participants will be identified by specialists in neurology and rehabilitation from inpatients at the Department of Acute Care, Department of Neurology, Thomayer University Hospital or University Hospital Kralovske Vinohrady, Prague, Czech Republic.

Inclusion criteria: Adults (18 - 85 years) after the first ischemic stroke in early sub-acute phase (40, 41), with a slight to moderately severe disability [2 - 4 on the Modified Rankin Scale (42)],

with minimal or moderate motor deficit of upper or lower extremities (on NIHSS Item 5 or 6 scores 1–3 points) who were able to perform activities of daily living prior to stroke event [0 – 2 on the Pre-Stroke Modified Rankin Score (43)], with a potential to accept 4 hours of comprehensive rehabilitation per day and to profit from the physiotherapy. Czech is their native language or its knowledge is at the level of the mother tongue.

Exclusion criteria: Low level of consciousness (vegetative state and/or minimally conscious state); severe cognitive decline that would interfere with administration of the tests, premorbid illiteracy, severe visual and/or auditory deficit that would prevent proper completion of the tests; behavioural disorders and/or lack of cooperation with therapist; and severe medical problems with a poor prognosis, (e.g., severe frailty, advanced and incurable cancer, fracture, cardiovascular disorders as chronic heart failure NYHA III, IV, symptomatic coronary artery disease Angina Severity Class III, IV, respiratory insufficiency as chronic obstructive pulmonary disease GOLD IV, and other severe disease) (44).

Randomisation

All patients meeting the above criteria will be invited to participate and asked to provide a written informed consent. They will be randomly assigned (1:1:1:1) as soon as possible, but always within 48 hours of admission, into one of the four interventions (represented by Group 1, 2, 3 or 4) using offsite-independent randomization protocols (www.randomization.com). Concealed allocation will be performed using sequentially numbered opaque sealed envelopes only accessible by research personnel with no involvement in the trial.

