2.8. Hypotheses

This clinical trial will test the following scientific hypotheses:

I. COMIRESTROKE under all three settings has a positive influence on all outcomes and higher effect than control group.

II. COMIRESTROKE - ICF will have the highest impact on primary outcomes (GAS, PROMIS, WHODAS 2.0) and on such secondary outcomes that were identified as treatment goals. Furthermore, we expect the highest impact on the primary outcomes in the follow-up (three and twelve months after finishing the rehabilitation).

III. COMIRESTROKE – NEFI will have the highest effect on the secondary outcomes, mainly on motor functions. Moreover, it will most significantly lead to the initiation of plastic and adaptive processes, assessed by the level of lncRNAs in the peripheral blood.

IV. The most important predictor of effective rehabilitation will be the level of disability at admission time; however, the content of the rehabilitation will have an impact on perceived, clinical, and physiological changes of the rehabilitant.

The exploratory goals of this clinical trial are as follows:

Goal I - Improvement patterns: Considering the high number of measured outcomes, for a deeper understanding of therapy efficacy with respect to patient and treatment characteristics, this clinical trial will aim to identify groups of patients with similar improvement patterns post therapy.

Goal II - Item-level analysis: To provide a deeper understanding of the differences in effectiveness between the three therapeutic approaches, this clinical trial will plan to explore item-level between-group differences in improvement.

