2.9. Measuring the effectiveness of rehabilitation

To test hypothesis I., i.e., a positive influence on all outcomes, the effect of therapy for each therapeutic group will be assessed separately by paired t-tests performed on pre-test and post-test scores. The Wilcoxon rank test will be used on data where normal distribution cannot be expected.

To test hypotheses II. and III, a comparison between therapeutic groups will be performed using two sample Student t-tests on differences between measurement time points (or Wilcoxon tests respectively for data, where normal distribution of the differences cannot be expected). For hypothesis II, the COMIRESTROKE - ICF group will be compared against the rest of the participants. For hypothesis III, the COMIRESTROKE - NEFI group will be compared against the rest of the participants. A one-sided alternative will be tested according to our hypotheses. We will also implement the one-way ANOVA test to jointly compare all three groups for prepost differences. In addition, a Tukey post-hoc comparison will be made to detect any further group differences beyond our hypotheses.

To assess the overall impact of rehabilitation and to compare effectiveness of different therapeutic approaches for Hypotheses I – III in more complex way, and to test for effect of other covariates in Hypothesis IV, a linear mixed effect model will be used with random patient effect fitted to longitudinal patient data. Measurement effect, group effect and their interaction, as well as effects of other covariates such as the level of disability in admission time will be tested by F test.

To address Goal I, correlations between changes in different examination scores will be evaluated using Pearson correlation coefficient and its nonparametric analogies. A cluster analysis will be performed to identify different phenotypes. This will allow the identification of different groups of patients in relation to the efficacy of the neuro-rehabilitation programs.

To address Goal II, for selected multi-item instruments, item-response theory (IRT) and generalized linear regression models will be used to study differential item functioning with respect to rehabilitation groups. Account will be taken for other respondent characteristics. Use will be made of differential item functioning in change (DIF-C) analysis (7) in order to detect between-group differences.

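### The sample size of 210 is three groups of 70, but the trial randomises equally to four arms, so the total, the number of arms and the per-group figure cannot all be right

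*Combined protocol and SAP*

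**What the plan says.** Section 2.6 (Estimated size) gives the recruitment rate, the total and the per-group number:

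- "It is estimated that approximately 110 people will be recruited to the clinical trial each year"
- "A total of 210 people is expected to be enrolled in the clinical trial over a period of two years"
- "corresponding to a required sample number of 70 patients per group"

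It justifies the 70 as the number needed to detect a difference "between two groups when achieving a mean difference effect" of Cohen's d = 0.5 at alpha = .05 with power .80. It gives neither the sidedness nor an allowance for dropout.

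The design sections count four groups. Section 2.1: "This will be a Four-Arm Parallel-Group Randomised Double Blinded Controlled Trial", with Group 4 receiving standard care as the comparator. Section 2.2, on randomisation: "They will be randomly assigned (1:1:1:1) as soon as possible", to one of four interventions.

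Hypothesis I in section 2.8 needs the control arm: "COMIRESTROKE under all three settings has a positive influence on all outcomes and higher effect than control group". Section 2.9 compares the ICF arm (hypothesis II) and the NEFI arm (hypothesis III) each with the remaining participants, and adds: "A one-sided alternative will be tested according to our hypotheses". It also plans a one-way ANOVA described as covering three groups, with Tukey post-hoc comparisons.

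**The concern.** A total of 210 that corresponds to 70 per group implies three groups, and the trial has four. One of the three figures must therefore be wrong: the total, the per-group number or the arm count. The documents do not show which. The 70 is called required and the 210 expected, and the mention of three groups in the ANOVA leaves open whether the sizing was done without the control arm.

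The recruitment target, the randomisation list and the reported power all depend on these figures. If 210 patients are enrolled, each arm has a quarter fewer patients than section 2.6 calls necessary (52.5 / 70 = 0.75). A reader who takes the stated 80% power at face value could then be misled about any comparison of one arm with another, including programme against control.

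**Working it through.** **Inputs.** From section 2.6: total 210, 70 per group, d = 0.5, alpha = .05, power .80, 110 recruits per year. From sections 2.1 and 2.2: four arms, 1:1:1:1. Loss rates and the effect size for arm-versus-rest contrasts are not in the documents; the values used below are assumptions.

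**1. The count.**
- 210 / 70 = 3 groups.
- 210 / 4 = 52.5 per arm.
- 4 × 70 = 280.
- 210 / 110 = 1.91 years; 280 / 110 = 2.55 years.

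This step needs no power formula, and it establishes the contradiction.

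**2. Trying to reproduce 70 per group.** The normal approximation is n = 2(z_alpha + z_beta)² / d².
- Two-sided: 2 × (1.960 + 0.842)² / 0.25 = 62.8, so 63. The noncentral t gives 63.8, so 64.
- One-sided: 2 × (1.645 + 0.842)² / 0.25 = 49.5, so 50. The noncentral t gives 50.2, so 51.

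Neither is 70. Seventy is 64 with about 9% added (70 / 64 = 1.094), equivalent to an 8.6% loss (1 − 64/70), but no such allowance is stated. Over four arms the stated inputs need 4 × 64 = 256 two-sided or 4 × 51 = 204 one-sided.

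**3. Power for one arm against another.** Noncentral t with noncentrality d√(n/2) and 2n − 2 degrees of freedom. At n = 52.5 the noncentrality is 0.5 × √26.25 = 2.56; at n = 70 it is 0.5 × √35 = 2.96.

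| Patients per arm | Two-sided | One-sided |
|---|---|---|
| 70 | 0.836 | 0.903 |
| 52.5 (210 over four arms) | 0.718 | 0.816 |
| 47.25 (10% loss, assumed) | 0.672 | 0.779 |
| 42 (20% loss, assumed) | 0.620 | 0.735 |

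With 52.5 per arm, 80% power needs d = 0.55 two-sided or 0.49 one-sided. One-sided power falls below 80% once loss exceeds 1 − 50.15/52.5 = 4.5%.

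**4. Power for one arm against the rest (hypotheses II and III).** If the rest means all three other arms, the contrast is 52.5 against 157.5 and the noncentrality is 0.5 × √(52.5 × 157.5 / 210) = 3.14.

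| Assumption | Two-sided | One-sided |
|---|---|---|
| d = 0.5, no loss | 0.878 | 0.931 |
| d = 0.5, 10% loss | 0.842 | 0.907 |
| d = 0.5, 20% loss | 0.797 | 0.875 |

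At d = 0.4, one-sided, power is 0.804 with no loss and 0.723 with 20% loss.

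If the rest means only the other two programmes (52.5 against 105), d = 0.5 gives 0.84 two-sided and 0.90 one-sided with no loss.

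**The case against.** The arithmetic itself is not open to dispute; the objections concern its consequences.

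**A one-sided reading rescues 210.** Section 2.9 states one-sided testing, and one-sided the inputs need 51 per arm, or 204 in four arms. On that reading only the 70 is wrong. This stands as far as it goes, so both sidedness figures belong in any restatement. But the one-sided sentence belongs to the arm-versus-rest tests, which are not the two-group contrast that section 2.6 sizes, and the margin is gone after about 4.5% loss in a trial with follow-up to one year.

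**The pairwise power matches no clearly planned test.** Section 2.9 tests hypothesis I with paired tests within each group and a mixed model. Its arm-against-arm comparisons are Tukey post hoc, with an adjusted threshold. This is fair: 72% and 82% describe the calculation in section 2.6 and not the power of the full analysis. They remain the right figures for checking the claim that section 2.6 makes.

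**The 2.5 years is conditional.** The 110 per year rests on one hospital's report, while section 2.2 recruits from two. Section 2.6 nevertheless presents 110 as the rate for the trial, so 2.5 years follows from the stated rate. If the second site adds patients, the time would be shorter.

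**Three groups in the ANOVA may just mean the three programmes.** That is possible. The contradiction does not depend on it.

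**The main tests are not short of power.** This is true for the one-sided arm-versus-rest tests if d = 0.5 applies to them. It limits the consequence without repairing the sample-size statement. Figure 2, on recruitment and randomisation, was not available to check, but no figure can make 210 equal 4 × 70.

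**Conclusion.** The concern holds. A total of 210, 70 per group and four equal arms are incompatible, and nothing in the text reconciles them. The gap is 17 to 18 patients per arm, or 70 patients in total.

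If 210 is the real target, power for one arm against another at d = 0.5 is about 72% two-sided, below the stated 80%, or 82% one-sided with almost no room for dropout. Hypotheses II and III, tested one-sided against all other participants, have about 93% power if d = 0.5 applies to that contrast, and about 80% if d is 0.4, both before loss.

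The contradiction in the count rests on no assumption. The power figures assume equal arms, a two-sample t-test with no multiplicity adjustment and, where shown, loss rates that the documents do not give. The statement must be corrected because it is the trial's only justification of its size.

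**What to change.** Reconcile the total, the number of arms and the per-group number in section 2.6 by one of two routes.

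(a) **Keep 210.** Replace 70 per group with 52–53 per arm. Restate the power for two arms at d = 0.5 as about 72% two-sided (80% at d = 0.55) or about 82% one-sided, before dropout, according to the sidedness chosen. This costs protocol wording only, plus a less favourable power statement if the test is two-sided.

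(b) **Keep 70 per arm.** Correct the total to 280 and the recruitment period to about 2.5 years at 110 per year, after confirming whether that rate covers both hospitals. This costs 70 more patients and, at the stated rate, roughly half a year more recruitment than the two years planned.

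On either route, section 2.6 should name the contrast being sized, its sidedness and the attrition allowance. It should report power separately for the arm-versus-rest tests of hypotheses II and III, with the effect size assumed for that contrast and a statement of whether the rest includes the control arm. Section 2.9 should say which groups enter the ANOVA, so that the group count is the same throughout.

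### The 70 per group in section 2.6 does not follow from its stated inputs, which give 64 (two-sided, two equal groups); the sidedness, contrast and any loss allowance are not stated

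*Combined protocol and SAP*

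**What the plan says.** Section 2.6 (Estimated size) plans the enrolment as follows: "A total of 210 people is expected to be enrolled in the clinical trial over a period of two years", "corresponding to a required sample number of 70 patients per group". It attributes that number to detecting a difference in improvement "between two groups when achieving a mean difference effect" of Cohen's d = 0.5, at a significance level of .05 and power of .80. It does not say whether the test is one- or two-sided, and it gives no allowance for loss or for multiple testing.

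Section 2.9 (Measuring the effectiveness of rehabilitation) plans, for Hypotheses II and III, "two sample Student t-tests on differences between measurement time points", with Wilcoxon tests where normality is doubtful. Each of these tests sets one arm (ICF or NEFI) against all other participants pooled. For them, "A one-sided alternative will be tested according to our hypotheses". The same section also plans a one-way ANOVA, Tukey comparisons and mixed-model F tests, which are not one-sided.

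The Randomisation paragraph in section 2.2 allocates 1:1:1:1 to four groups.

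**The concern.** Once the sidedness is chosen, d, alpha and power fix the size of a two-group t-test. Section 2.6 gives all three and presents 70 as the number they require, yet 70 is neither the two-sided nor the one-sided answer. A reader cannot tell whether 70 means evaluable patients, or a smaller evaluable number plus an undeclared margin. That distinction matters because the primary outcomes are followed to one year (sections 2.1 and 2.4), so some loss is to be expected.

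Nor can a reader tell which comparison has the stated 80% power. Section 2.6 describes two groups and is silent on sidedness. Section 2.9 uses a one-sided alternative for some tests and not for others, and those one-sided tests do not compare two equal groups.

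**Working it through.** **Inputs.** From 2.6: d = 0.5, alpha = .05, power = .80, two groups, 70 per group, 210 in total. From 2.2: four arms, equal allocation. From 2.9: the t-test on change scores, the one-sided alternative for Hypotheses II and III, and the one-against-the-rest contrast.

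**The plan's own figures.** 3 × 70 = 210, so the total is three groups of 70. The 70 itself is not reproduced by the steps below.

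**Two equal groups, normal approximation.** n per group = 2(z_alpha + z_beta)²/d².
- Two-sided: 2(1.960 + 0.842)²/0.25 = 62.8, so 63.
- One-sided: 2(1.645 + 0.842)²/0.25 = 49.5, so 50.

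**Two equal groups, exact noncentral t.**

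| Test | n solved | n per group | Power at 70 per group |
|---|---|---|---|
| Two-sided | 63.77 | 64 | 83.6% |
| One-sided | 50.15 | 51 | 90.3% |

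Read the other way, 70 per group gives 80% two-sided power at d = 0.477, not 0.5.

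**What would produce 70.** Each route needs an input that 2.6 does not give.
- Loss allowance on the two-sided figure: 63/0.90 = 70, or 64/0.92 = 69.6, rounded up to 70. If 64 is the evaluable number, the loss covered is 1 − 64/70 = 8.6%.
- One-sided test at 90% power: 69.2, rounded up to 70.
- The Wilcoxon fallback at an assumed relative efficiency of 0.955 does not reach 70: 63.77/0.955 = 66.8, so 67 two-sided; 50.15/0.955 = 52.5, so 53 one-sided.

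**The one-sided contrast in 2.9.** This is one arm against the pooled rest. With r patients in the rest for each patient in the single arm, the approximation is n = (1 + 1/r)(z_alpha + z_beta)²/d². Assuming d = 0.5 applies to this contrast:
- r = 2 (rest is two arms): approximation 37.1; exact t 37.55, so 38 in the single arm.
- r = 3 (rest is three arms): approximation 33.0; exact t 33.32, so 34 in the single arm.

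These are not 70 either, and they are not 51.

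**Power at the number planned per arm.** 210/4 = 52.5 per arm. For two equal arms at d = 0.5 and before any loss, exact t gives 71.8% two-sided and 81.6% one-sided. The stated 80% lies between the two.

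**The case against.** The strongest reply is that two-sided testing is the natural reading of the comparison in 2.6. On that reading 70 exceeds 64 by six patients per group and errs on the conservative side. A loss of 8 to 10% would take 63 or 64 to about 70, and the Wilcoxon fallback alone would need about 67. The gap is thus no larger than an ordinary planning margin, and 70 evaluable per group would not underpower the stated comparison. This stands as to size. It does not explain the figure: neither margin is documented as its source, and 2.6 attributes 70 to d, alpha and power alone.

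A reader might go further and take 51 as the requirement of the one-sided tests in 2.9, so that four arms need 4 × 51 = 204 of the 210 and under 3% is left for loss. The documents do not support that. The one-sided alternative is limited to Hypotheses II and III, and those tests compare one arm with the pooled rest, for which about 38 or 34 in the single arm would suffice if d = 0.5 applies. The 51 belongs only to a one-sided comparison of two equal groups.

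It may also be said that the larger defect in 2.6 is the total built on three groups when four are randomised. That is a separate matter. It bears on this point only because it sets the number per arm at which power should be reported.

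**Conclusion.** The point holds as a correction to a stated figure. The inputs in 2.6 give 64 per group two-sided, or 51 one-sided for two equal groups; 70 follows from neither. With 70 evaluable per group the power would be 83.6% or 90.3%, not 80%. If 70 conceals a loss allowance on 64, it covers 8.6%; that origin is an assumption.

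The discrepancy of six per group is small and conservative, and it would be wrong to infer from it that the two-group comparison is underpowered at 70. The practical weight lies in the missing sidedness. At about 52 per arm, two equal arms have about 72% power two-sided and 82% one-sided, so the claim of 80% fails on one reading and holds on the other. These figures assume d = 0.5, equal arms, a t-test on change scores, no loss and no adjustment for multiple tests.

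**What to change.** Rewrite the paragraph in 2.6 so that it:
1. names the contrast being powered (two arms, or one arm against the rest) and its sidedness, consistent with 2.9;
2. gives the evaluable number for that contrast, which is 64 per arm for a two-sided comparison of two equal arms at d = 0.5;
3. states any loss allowance separately, as n/(1 − loss), with the assumed loss rate;
4. replaces the stated 80% with the power at the number actually planned per arm. For 210 patients in four arms this is about 72% two-sided or 82% one-sided for two equal arms, before loss.

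If a one-against-the-rest test from 2.9 is chosen as the powered contrast, its own n should be given together with the effect size assumed for it; the 51 should not be used there.

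The cost is one paragraph. Correcting the statement requires no added enrolment. Whether the sponsor then accepts the power so reported is a separate decision.

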Ischemic stroke causes an extensive range of clinical dysfunctions. To narrow the program, motor disability was chosen as one of the inclusion criteria, as it is the most common and widely recognised problem (8). Motor recovery provides a direct means of addressing the effectiveness of therapy. Nineteen intervention types relevant to motor recovery after stroke have been identified (8). The most commonly applied include those involving Motor/Skill acquisition and Technology-based individualized interventions where the patient is increasingly active in the motor re-training process and the principles of sensory-motor learning are applied. Neurophysiological approaches including Bobath which stimulate neuroproprioceptive "facilitation, inhibition" (106, 107), are rarely utilised. In the Czech Republic, Vojta reflex locomotion, is routinely used in clinical practice. To date, only one very recent study has documented its effectiveness in stroke patients (108). This clinical trial should confirm this promising finding, and moreover enable the comparison of its effectiveness with alternative rehabilitation approaches implementing technology-based physiotherapy as well as those applying the ICF model. Importantly, this clinical trial will enable the systematic collection of demographics, biometric and molecular marker information allowing an opportunity for association analysis that may provide further evidence identifying indicators of effective rehabilitation. It is expected that the treatment will be much more effective in patients who start the rehabilitation soon after the ischemic stroke event. Patients will be scored for disability, personality traits, cardiovascular function and cognitive ability as outlined above.

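### The 80% power in section 2.6 describes one unadjusted comparison of two arms, which section 2.9 never makes; the tests that are planned have quite different power

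*Combined protocol and SAP*

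**What the plan says.** Section 2.6 gives a total of 210 patients and 70 per group. It explains: "This value is necessary in order to detect a significant difference in improvement" "between two groups when achieving a mean difference effect", with Cohen's d = 0.5, alpha .05 and power .80. It names no test, no side, no multiplicity adjustment and no dropout allowance.

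Section 2.9 then plans:

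- Hypothesis I: paired t-tests of pre against post, within each arm.
- Hypotheses II and III: two-sample t-tests on change scores, one-sided, comparing ICF (II) or NEFI (III) with all remaining participants.
- A joint test: "We will also implement the one-way ANOVA test to jointly compare all three groups for prepost differences".
- Pairwise comparisons: "In addition, a Tukey post-hoc comparison will be made to detect any further group differences beyond our hypotheses".
- A linear mixed model in which the group, measurement and interaction effects are assessed by F tests. No pairwise contrast is named.

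Wilcoxon tests replace the t-tests where normality cannot be assumed. The Discussion (section 3) expects the trial to support the evidence for Vojta reflex locomotion and to "enable the comparison of its effectiveness with alternative rehabilitation approaches implementing technology-based physiotherapy as well as those applying the ICF model".

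**The concern.** A reader of 2.6 takes the trial to have 80% power to separate any two arms that differ by half a standard deviation in improvement. Section 2.9 has no such test. The hypothesis tests use another contrast (one arm against a pooled rest) and are one-sided. The one procedure that sets a single arm against another is Tukey-adjusted, so its critical value is higher than that of a plain t-test.

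This matters in two ways. A non-significant difference between two programmes may be reported as a negative result with 80% power, which it would not be. And the power of the tests that carry Hypotheses II and III is not stated at all, although it depends strongly on how the arms differ from one another.

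**Working it through.** **Inputs.** From 2.6: d = 0.5 (SD set to 1), alpha .05, power .80, 70 per group, 210 in total. From 2.2: allocation 1:1:1:1 to four arms, so 210/4 = 52.5 per arm. From 2.9: the tests, the one-sided alternative, and the three groups named for the ANOVA. My assumptions: normal data, equal variances, no dropout, one outcome at a time.

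**Step 1: the plan's own figure.** For two groups of n, the noncentrality is 0.5 × √(n/2) on 2(n−1) degrees of freedom.

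- Two-sided .05, 80% power: 64 per group (63 by the normal approximation). One-sided: 51 (50).
- At n = 70: noncentrality 0.5 × √35 = 2.958, two-sided critical value 1.977, power 83.6%. One-sided power is 90.3%.

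So 70 is not what the stated inputs give. An unstated allowance of about 10% for dropout would produce it (63/0.9 = 70), but that is a guess. Either way, the calculation is for one unadjusted comparison of two arms.

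**Step 2: one arm against the rest, one-sided .05 (Hypotheses II and III).** The noncentrality is δ × √(n1·n2/(n1+n2)), where δ is the difference from the mean of the rest. If the arm is 0.5 above that pooled mean, δ = 0.5. If it exceeds only one other arm by 0.5 and equals the others, δ = 0.5/2 = 0.25 with two other arms, or 0.5/3 = 0.167 with three.

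| Arm v rest | Power, δ = 0.5 | Power, only one arm differs |
|---|---|---|
| 70 v 140 (three groups) | 96.1% | 52% |
| 70 v 210 (four groups) | 97.6% | 33% |
| 52.5 v 157.5 (four groups, 210 in total) | 93.1% | 27% |

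The last column takes the SD within the rest as 1. Mixing unequal arms widens it slightly, so those figures are, if anything, a little high.

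**Step 3: Tukey, one named pair, familywise .05 two-sided.** The critical value is q(.95; k, k(n−1))/√2, where q is the studentized range quantile. Power is the tail of the noncentral t with k(n−1) degrees of freedom and noncentrality 0.5 × √(n/2), which is 2.958 at n = 70 and 2.562 at n = 52.5.

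| Groups in family | n per group | Critical value | Power at d = 0.5 | d detectable with 80% |
|---|---|---|---|---|
| 3 | 70 | 2.361 | 72.4% | 0.54 |
| 3 | 52.5 | 2.367 | 57.8% | 0.63 |
| 4 | 70 | 2.585 | 64.6% | 0.58 |
| 4 | 52.5 | 2.590 | 49.0% | 0.67 |

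Simulation for three groups of 70 gives 72.3%. For 80% power per pair, Tukey needs 83 per group (three groups) or 94 (four).

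**Step 4: what Tukey itself costs.** At 70 per group the like-for-like loss is from 83.6% to 72.4%, about 11 points. Against the stated 80% it is about 8 points.

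**The case against.** The strongest reply is that the sample size should not be judged by Tukey. Section 2.9 puts that step outside the hypotheses, and 2.6 claims no power for it. The tests of Hypotheses II and III are two-group t-tests of improvement with no stated adjustment, which is close to the form in 2.6, and they exceed 90% power when d = 0.5 is measured from the pooled rest. This stands. A reader might infer that the trial as a whole has only 72% power, or that its main tests are underpowered; the documents do not support that. What remains is that the contrast and the side differ from those in 2.6, and that the power above 90% disappears if only one other arm differs.

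Second, 72% is for one named pair. If one arm exceeds both others by 0.5 (three groups of 70), the chance that Tukey finds at least one of the two differences is 86%, and both 59%. This also stands, so the success criterion should be stated with the figure.

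Third, the Discussion promises no powered pairwise test, and the mixed model could estimate pairwise contrasts. True, but 2.9 names none, so Tukey is the only arm-against-arm procedure actually written down.

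Fourth, the 58% and 49% figures rest on 52.5 per arm, which comes from a separate inconsistency between four arms and 3 × 70 = 210. They should not be charged to Tukey.

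Finally, one might want to replace Tukey by an F test followed by unadjusted pairwise t-tests. For three groups of 70 the gain is about 2 to 8 points, depending on where the third arm lies. The approach gives up matching simultaneous intervals, and it does not control familywise error with four groups. Tukey is valid, and nothing in the documents calls for replacing it.

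**Conclusion.** The point holds as a mismatch between 2.6 and 2.9. The stated 80% belongs to an unadjusted comparison of two arms that the plan does not make. The planned one-sided tests of one arm against the rest have 93-98% power if d = 0.5 is the distance from the pooled rest, and 27-52% if only one other arm differs by 0.5. The supplementary pairwise comparison has 72% per named pair in the most favourable reading (three groups of 70), and less if Group 4 enters or arms hold about 52 patients.

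These figures assume normal change scores, equal variances and no dropout. The documents do not say which pattern of arm means is expected, so the range for the one-against-rest tests is wide. No test in 2.9 is shown to be invalid. The defect is a power statement that does not say what it covers, and it should be corrected.

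**What to change.** In 2.6:

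1. State that the 80% refers to one unadjusted comparison of two arms, give its side, and explain why 70 rather than 64 (two-sided) is used.
2. Add the power of the one-sided tests of one arm against the rest: 93-98% if d = 0.5 is the difference from the pooled rest; 52% (three groups of 70), 33% (four of 70) or 27% (four of 52.5) if the arm exceeds only one other arm by 0.5. Say which pattern is assumed.
3. Add the power of the Tukey comparison for one named pair: 72% for three groups of 70 (detectable d 0.54), with the lower figures from the table if Group 4 is included or arms hold about 52 patients.

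In 2.9, keep Tukey and add that non-significant pairwise results will not be presented as 80%-powered; report them with their simultaneous confidence intervals.

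The cost is a few sentences, with no extra patients or data. The price is a less favourable power statement for the pairwise comparison of programmes. The final figures also depend on settling the number of groups and patients per arm, which is a separate correction.
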